5.3.3 Management of Results

We plan to contact participants if a clinically actionable gene variant is discovered. Clinically actionable findings for the purpose of this study are defined as disorders appearing in the American College of Medical Genetics and Genomics recommendations for the return of secondary findings that is current at the time of primary analysis. (A list of current guidelines is maintained on the CCR intranet:

<https://ccrod.cancer.gov/confluence/display/CCRCRO/Incidental+Findings+Lists>). Unless requested otherwise, participants will be contacted at this time with a request to provide a sample to be sent to a CLIA certified laboratory.

5.3.4 Genetic counseling

If the research findings are verified in the CLIA certified lab, the participant will be offered the opportunity schedule a visit, in person (at our expense) or via telemedicine on an NIH approved platform to have genetic education and counseling to explain this result. If the subject does not want to come to NIH, a referral to a local genetic healthcare provider will be provided (at the participant's expense).

The expenses related to verification of results in a CLIA certified laboratory and genetic counseling performed at the NIH will be funded by the Center for Cancer Research.

This is the only time during the course of the study that incidental findings will be returned. No interrogations regarding clinically actionable findings will be made after the primary analysis.

Participants will be requested to maintain up to date contact information to enable future contact.

We also plan to obtain permission from the participants at the time of consent to release results regarding incidental findings in the event the patient dies before results are available. The participant may designate the appropriate blood relative to be contacted if the patient is dead or unavailable in a signed written release of medical information request.

6 DATA COLLECTION AND EVALUATION

6.1 DATA COLLECTION

The PI will be responsible for overseeing entry of data into a 21 CFR Part 11-compliant data capture system provided by the NCI CCR and ensuring data accuracy, consistency and timeliness. The principal investigator, associate investigators/research nurses and/or a contracted data manager will assist with the data management efforts. Primary and final analyzed data will have identifiers so that research data can be attributed to an individual human subject participant.

All adverse events, including clinically significant abnormal findings on laboratory evaluations, regardless of severity, will be followed until return to baseline or stabilization of event.

Document AEs from the through 90 days after the intervention was last administered. During the study follow up period (following collection of AEs for MTD), only adverse events which are serious and related to the study intervention (radiation and 18F-DCFPyL) need to be recorded.

An abnormal laboratory value will be recorded in the database as an AE **only** if the laboratory abnormality is characterized by any of the following:

- Results in discontinuation from the study
- Is associated with clinical signs or symptoms
- Requires treatment or any other therapeutic intervention
- Is associated with death or another serious adverse event, including hospitalization.
- Is judged by the Investigator to be of significant clinical impact
- If any abnormal laboratory result is considered clinically significant, the investigator will provide details about the action taken with respect to the test drug and about the patient's outcome.

End of study procedures: Data will be stored according to HHS, FDA regulations, and NIH Intramural Records Retention Schedule as applicable.

Loss or destruction of data: Should we become aware that a major breach in our plan to protect subject confidentiality and trial data has occurred, this will be reported expeditiously per requirements in section [7.2.1](#).

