3.1.1 Dose Limiting Toxicity

Dose-limiting toxicities will be defined as follows (during treatment and within the first three weeks after treatment):

- Grade 3 rectal, small bowel, or urinary toxicity that does not resolve to Grade 2 or less within 4 days with appropriate medical management
- Other grade 3 in-field toxicities attributable to SBRT that do not resolve to Grade 2 or less within 4 days with appropriate medical management
- Delays of more than one week in completing radiation treatment due to toxicity (cumulative duration of delay over the course of the entire treatment).

Additionally, late toxicities (those that occur after 90 days following completion of treatment) will be followed and scored but will not be used for escalation with the following exception.

If Grade ≥ 4 late bowel or Grade ≥ 3 bladder injury is observed in 2 patients in any cohort, dose escalation will be terminated in that arm and the dose below that dose level in which the toxicity was observed will be considered the MTD. The criteria for late DLT for bladder were changed to Grade 3 to Grade 4 via amendment version date 04/13/2021, and should apply retroactively to all prior participants. MTD will be determined for each arm separately. Early and late toxicities used for assessment of DLTs should be attributable (possible, probable or definite) to SBRT. Changes in sexual and erectile function will not be considered a DLT.

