6.1.1 Clinical Data

Clinical data including summary and demographic data will be collected and entered into a 21 CFR Part 11-compliant data capture system provided by the NCI CCR. Data capture will include baseline and follow up PSA values, testosterone values, use of ADT, presence or absence of biochemical relapse, and questionnaire scores.

Imaging data will include storage of the reconstructed images and image derived parameters on a secure, password protected lab imaging database. Images may also be stored in the clinical center PACS. The lab imaging database will be stored and maintained in the Molecular Imaging Branch facilities. Personal identifiers will not be used when storing imaging data.

NCI Molecular Imaging Branch may exchange anonymized clinical data with working groups, and qualified investigators. The anonymized image data will be stored in an existing secure off-

site imaging database (EXEC PACS) and these images may be shared with researchers at other institutions.

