8.1.2 Serious Adverse Event (SAE)

An adverse event or suspected adverse reaction is considered serious if in the view of the investigator or the sponsor, it results in any of the following:

- Death,
- A life-threatening adverse event (see section [8.1.3](#))
- Inpatient hospitalization or prolongation of existing hospitalization
 - A hospitalization/admission that is pre-planned (i.e., elective or scheduled surgery arranged prior to the start of the study), a planned hospitalization for pre-existing condition, or a procedure required by the protocol, without a serious deterioration in health, is not considered a serious adverse event.
 - A hospitalization/admission that is solely driven by non-medical reasons (e.g., hospitalization for patient or subject convenience) is not considered a serious adverse event.
 - Emergency room visits or stays in observation units that do not result in admission to the hospital would not be considered a serious adverse event. The reason for seeking medical care should be evaluated for meeting one of the other serious criteria.

- Persistent or significant incapacity or substantial disruption of the ability to conduct normal life functions
- A congenital anomaly/birth defect
- Important medical events that may not result in death, be life-threatening, or require hospitalization may be considered a serious adverse drug experience when, based upon appropriate medical judgment, they may jeopardize the patient or subject and may require medical or surgical intervention to prevent one of the outcomes listed in this definition.

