8.2 ASSESSMENT OF SAFETY EVENTS

AE information collected will include event description, date of onset, assessment of severity and relationship to study product and alternate etiology (if not related to study product), date of resolution of the event, seriousness and outcome. The assessment of severity and relationship to the study product will be done only by those with the training and authority to make a diagnosis and listed on the Form FDA 1572 as the site principal investigator or sub-investigator. AEs occurring during the collection and reporting period will be documented appropriately regardless of relationship. AEs will be followed through resolution.

SAEs will be:

- Assessed for severity and relationship to study product and alternate etiology (if not related to study product) by a licensed study physician listed on the Form FDA 1572 as the site principal investigator or sub-investigator.
- Recorded on the appropriate SAE report form, the medical record and captured in the clinical database.
- Followed through resolution by a licensed study physician listed on the Form FDA 1572 as the site principal investigator or sub-investigator.

For timeframe of recording adverse events, please refer to section **6.1**. All serious adverse events recorded from the time of first investigational product administration must be reported to the sponsor.

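### Section 6.1 does not clearly require recording of the non-serious late Grade 3 bladder events that section 3.1.1 counts toward an arm's MTD

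*Combined protocol and SAP*

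**What the plan says.** Section 3.1.1 states that "late toxicities (those that occur after 90 days following completion of treatment) will be followed and scored". They do not drive escalation, with one exception: "If Grade ≥ 4 late bowel or Grade ≥ 3 bladder injury is observed in 2 patients in any cohort", escalation stops in that arm and the dose level below becomes the MTD. The events must be at least possibly attributable to SBRT; nothing requires them to be serious. The April 2021 amendment lowered the urinary criterion from Grade 4 to Grade 3 (section 1.2.5), and the change "should apply retroactively to all prior participants".

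Section 6.1 documents adverse events "through 90 days after the intervention was last administered". In the follow-up period after that, "only adverse events which are serious and related to the study intervention (radiation and 18F-DCFPyL) need to be recorded". A parenthesis places this period after adverse events have been collected for the MTD. The section does not name the late bladder and bowel events. Section 8.2 sets no competing period: "For timeframe of recording adverse events, please refer to section" 6.1.

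Section 8.1.2 defines serious by outcome: death, threat to life, admission, lasting or significant incapacity, and the like. Beyond these, "Important medical events that may not result in death, be life-threatening, or require hospitalization may be considered a serious adverse drug experience", which is a matter of judgment.

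**The concern.** The two sections apply different filters to the same period. After day 90, section 3.1.1 selects events by organ, grade and attribution; section 6.1 selects by seriousness and relatedness. A site that follows 6.1 to the letter can leave out events that 3.1.1 needs.

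Two results depend on those events. One is the late toxicity profile, part of a secondary objective (section 1.1.2). Section 10.4.4 codes each adverse event once per patient at its maximum severity in the assessment period, so a late event that was never recorded cannot contribute. The other is the late MTD rule, which feeds the primary endpoint. Its threshold is 2 patients, so a single unrecorded event can hold the documented count at 1. The error has one direction: leaving events out can only make the profile look milder and the rule fire less often.

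**Working it through.** The plan gives no figure for this point, so the check is a comparison of passages.

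1. **Boundary.** Late toxicity in 3.1.1 begins after 90 days from completion of treatment. General documentation in 6.1 ends 90 days after the last intervention. Taking the intervention to be SBRT, the narrower recording rule starts where the late rule starts.

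2. **Which events fall between the two rules.** For new-onset events after day 90 that are attributable to SBRT:

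| Event | Counts under 3.1.1 | Must be recorded under 6.1 |
|---|---|---|
| Bladder, Grade 3 or worse, serious | Yes | Yes |
| Bladder, Grade 3, not serious | Yes | No |
| Bowel, Grade 4 or worse, serious | Yes | Yes |
| Bowel, Grade 4 or worse, not serious | Yes | No, but few such events are likely |

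The second row is the gap. A bowel event of Grade 4 or worse will usually meet one of the outcomes in 8.1.2, so the bowel part of the rule is little affected.

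3. **Whether a Grade 3 bladder event can be non-serious.** Under 8.1.2 it can. No outcome there is defined by grade, and an emergency visit or observation stay without admission does not by itself qualify. Section 1.2.5 reports a transient Grade 3 hematuria and a Grade 3 urinary incontinence in Arm 1 at level 2. These are the kind of event in question, but their timing and seriousness are not given.

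4. **Span of the narrower rule.** The section 3.6 calendar has follow-up visits at months 1, 3, 6, 9, 12, 15, 18, 21 and 24, which is 9 visits. Those wholly after day 90 are months 6 to 24, which is 7. In days, 730 − 90 = 640, and 640/730 = 0.88. This is a share of calendar time only.

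5. **Where the MTD can still move.** Table 2 closes level 3 in both arms. Arm 1 is expanded at level 1, and Table 2 has no lower level. Arm 2 is expanded at level 2, with level 1 below it. At the October 2021 determination, 3 patients had entered Arm 2 level 2, one of them still on treatment, and toxicity in that arm had not exceeded Grade 2 urinary or Grade 3 bowel. Late data from that patient and from the expansion were still to come.

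**The case against.** The best defense is that the documents should be read together. Section 3.1.1 requires late toxicity to be scored, its trigger is injury that is observed rather than recorded, and 6.1 sets only a minimum. The parenthesis in 6.1 could be read as keeping MTD-relevant events in full collection. The calendar keeps adverse events under continuous monitoring and schedules clinical evaluations to month 24, and the principal investigator reviews each patient's data (7.4.1). Events that began before day 90 are followed until they resolve or stabilize. Some Grade 3 events will be serious because of admission or marked disruption of daily life. The team did identify the Arm 1 Grade 3 urinary events and amended the protocol because of them.

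Most of this stands, and it makes an unnoticed event less likely. It does not make grade, onset date and attribution required data for a non-serious event after day 90. The parenthesis is ambiguous: 6.1 gives no end date other than 90 days, and section 10.1 ties toxicity assessment for escalation to 3 weeks after SBRT, which favors the narrower reading.

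Two further inferences would go too far:

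- A reader might take the silence of 6.1.1 on late toxicity grades as evidence. That list contains no adverse event data at all, early or late, so the silence shows nothing.
- A reader might infer that the 6-month 18F-DCFPyL scan restarts the 90 days in rescanned patients, because 6.1 names the tracer as study intervention. Sections 3.1.1 and 3.10 count from completion of treatment or the last dose of study therapy, which points to SBRT. A restart would in any case lengthen full recording, not shorten it.

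**Conclusion.** The conflict is in the current text and should be fixed, but it is narrow. It concerns one class of event: new-onset, SBRT-attributable, non-serious Grade 3 bladder toxicity after day 90. The main consequence is a late toxicity profile that may be understated in both arms. For the MTD, what remains is mainly Arm 2 at level 2.

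This rests on two assumptions: that some late Grade 3 bladder events are non-serious, a share the documents do not give, and that recording follows the minimum in 6.1. The documents give no Arm 2 accrual or toxicity after October 2021, so the current state of that exposure is unknown.

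A reader might infer that events have been lost, that an MTD is wrong, or that 88% of late toxicity goes unrecorded. None of these follows. No missed event is shown, and the 88% measures follow-up time, not risk of data loss.

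**What to change.** Reconcile 6.1 with 3.1.1. State in 6.1 that bladder and bowel adverse events at the grades named in 3.1.1 are recorded with grade, onset date and attribution to SBRT through the 24-month visit, regardless of seriousness, and repeat this in a footnote to the 3.6 calendar. A bare cross-reference to 3.1.1 would remove the contradiction but would not say which items are recorded or until when. Because the criterion is retroactive, abstract the same items from existing charts for patients already treated.

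The cost is one or two sentences, a calendar footnote, a follow-up case report form page and a short chart abstraction. Clinical evaluations already run every 3 months to month 24, so no visit or procedure is added. The change concerns recording only; it alters neither the toxicity criterion nor any dose.

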3.6 STUDY CALENDAR

| Procedure | Screening/ Baseline | Active SBRT treatment | Post Therapy Follow-up (1, 3 mos) 15 | Post Therapy Follow-up 6 months post-SBRT | Post Therapy Follow-up (9 mos and q 3 mos until 24 mos) 8 | |
|--|------------------------|-----------------------------|---|--|---|--|
| History and PE | X | | | | | |
| Vital signs 10 | X | | X | X | X | |
| Performance Score | X | | | | | |
| Weight | X | | | | | |
| Labs | | | | | | |
| CBC, Acute care panel, LFTs, Testosterone, PT/PTT, Viral serologies 2 | X | | | | | |
| PSA 4 | X | | X 11 | X 11 | X 11 | |
| Biopsies (ultrasound guided)/fiducials 5 | X | | | | | |
| mpMRI 3 | X 3 | | | X 12 | | |
| 18F-DCFPyL PET/CT imaging | X 7 | | | X 6, 12 | | |
| 18F-NaF PET/CT imaging 3 | X | | | | | |
| Whole body bone scan 3 | X | | | | | |
| Clinical evaluation | | X | X 9 | X 9 | X 9 | |
| Adverse Events | X | | Monitored continuously | | | |
| Concomitant Medications | X | | Monitored continuously | | | |
| Correlatives | | | | | | |
| Research Biopsy 5 | X | | | | | |
| Blood 12 | X | X 1 | X | X | X | |
| Urine 12 | X | | X | X | X | |
| Questionnaires | | | | | | |
| EPIC-26, SHIM, AUA-SI, DRS, PROMIS 13, 14 | X | | X | X | X | |

1. Correlative blood sampling should be performed within 24 hours after the last dose of irradiation.
2. CBC with differential, chemistries (to include creatinine BUN, PSA, testosterone, Alk Phos, ALT, AST, Bilirubin), PT, PTT within 4 weeks of study entry. Viral serologies: HIV, Hepatitis B, and Hepatitis C screening within 4 weeks of study entry. Acute Care Panel: (Sodium (NA), Potassium (K), Chloride (CL) Total CO₂ (Bicarbonate), Creatinine, Glucose, Urea nitrogen, eGFR).
3. Whole body bone scan, F18 NaF PET, and multiparametric MRI of the prostate. In selected patients, a CT of the abdomen and pelvis (with oral and IV contrast) may also be obtained for staging, particularly if MRI is not felt to adequately have staged the pelvic and abdominal lymph nodes. All imaging studies should be completed within 3 months prior to study entry. MRI of the prostate obtained more than 3 months (no greater than 5 months prior to entry) may be used if a biopsy has recently been performed, as post-biopsy MRI may not be easily interpretable due to hemorrhage.

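### Section 6.1 does not require recording of non-serious late Grade 3 bladder events, although under 3.1.1 two patients with such events can set the MTD

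*Combined protocol and SAP*

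**What the plan says.** **The late rule.** Section 3.1.1 defines late toxicity as arising more than 90 days after treatment and keeps it out of escalation decisions, with one exception. The trigger is bowel injury of Grade 4 or worse, or bladder injury of Grade 3 or worse, in 2 patients. Escalation then stops in the arm concerned, and the rule also settles the primary result: "the dose below that dose level in which the toxicity was observed will be considered the MTD". The event must be possibly, probably or definitely attributable to SBRT. Seriousness is not a condition.

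**The recording rule.** Section 6.1 has adverse events documented "through 90 days after the intervention was last administered". After that its requirement narrows: "only adverse events which are serious and related to the study intervention (radiation and 18F-DCFPyL) need to be recorded". The opening of the same sentence, "During the study follow up period (following collection of AEs for MTD", uses a parenthesis to place the narrower rule after MTD collection. Section 8.2 sets no timeframe of its own; its cross-reference, "For timeframe of recording adverse events, please refer to section", is to 6.1.

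**Seriousness.** Section 8.1.2 defines it by outcome, not by CTCAE grade. Care that stops short of admission is not serious in itself ("Emergency room visits or stays in observation units that do not result in admission to the hospital would not be considered"), although the reason for the visit must still be checked against the other criteria. The important-medical-event criterion is a matter of judgment.

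**Current state.** Section 1.2.5 and the footnotes to Tables 2 and 4 say that neither arm will go to level 3. In Arm 1, level 1 is taken as the MTD under the amended late criterion. In Arm 2, level 2 is being expanded.

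**The concern.** The period in which a late event can count toward the MTD starts at the point where 6.1 narrows what must be recorded. The parenthesis in 6.1 treats collection for the MTD as already complete by then, whereas under 3.1.1 the late part of it is just beginning.

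The narrower rule falls mainly on Grade 3 bladder events. Grade 4 bowel events will usually be serious and so will usually be recorded. A Grade 3 haematuria managed without admission need not be serious, yet it qualifies under 3.1.1.

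The rule needs only 2 patients, so a single event missing from the record can decide whether the data show it as met. At stake is whether 42.5 Gy or 40 Gy is reported as the Arm 2 MTD, which is the primary objective.

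**Working it through.** **Step 1. Set the windows side by side.**

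| Period after SBRT | Role in the MTD | Recording required by 6.1 |
|---|---|---|
| Treatment to 3 weeks | Early DLT (3.1.1, 3.1.2, 10.1) | All adverse events |
| After 90 days, to 24 months | Late exception (3.1.1) | Serious and related events only |

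The whole late window lies in the reduced-recording period. It contains seven scheduled visits: month 6, then the column "Post Therapy Follow-up (9 mos and q 3 mos until 24 mos"), that is months 9, 12, 15, 18, 21 and 24.

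**Step 2. Find an event that counts but need not be recorded.** Take a Grade 3 bladder event at month 12, attributable to SBRT, managed without admission and not judged an important medical event. Under 3.1.1 it counts. Under 8.1.2 it is not serious. Under 6.1 it need not be recorded. The mismatch needs no numerical assumption.

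**Step 3. Bound the effect on the 2-patient rule.** The plan gives no figure to reproduce. Inputs:

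- *n*, patients at Arm 2 level 2: 9 (3 treated per 1.2.5, plus the 6 additional patients in Table 3) or 12 (a full group of 6, plus 6).
- *p*, late event rate per patient: 7% or 20%. The 7% is the Grade 3 or worse GU rate in the SBRT re-irradiation series described in 1.2.1 (2 of 29 = 6.9%). That series used a different regimen, and the figure is not restricted to late events. The 20% is an assumption.
- *q*, share of such events that are non-serious: not in the documents. Assumed 25%, 50% or 75%, independent between patients.
- Only what 6.1 requires is recorded. This makes the result an upper limit on the loss.

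With r = p(1 − q), the chance that required records show the rule as met is

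P(X ≥ 2) = 1 − (1 − r)^n − n·r·(1 − r)^(n−1).

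For n = 9, p = 0.07:

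- All recorded, r = 0.07: 1 − 0.5204 − 0.3525 = 0.127.
- q = 50%, r = 0.035: 1 − 0.7257 − 0.2369 = 0.037.

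| n | p | All recorded | q = 25% | q = 50% | q = 75% |
|---|---|---|---|---|---|
| 9 | 7% | 12.7% | 7.8% | 3.7% | 1.0% |
| 9 | 20% | 56.4% | 40.1% | 22.5% | 7.1% |
| 12 | 7% | 20.3% | 12.8% | 6.4% | 1.8% |
| 12 | 20% | 72.5% | 55.7% | 34.1% | 11.8% |

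At n = 9 and 7% the loss is 12.7 − 7.8 = 4.9 to 12.7 − 1.0 = 11.7 percentage points. At n = 12 and 20% it is 72.5 − 55.7 = 16.8 to 72.5 − 11.8 = 60.7 points.

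**The case against.** **The late rule runs on observation, not on the adverse event log.** Section 3.1.1 fires when injury is observed and orders late toxicity to be followed and graded. The calendar in 3.6 keeps adverse events under continuous monitoring, with a clinical evaluation at every follow-up visit. Section 7.4.1 has the investigator review each patient's adverse event data, and EPIC-26 and AUA-SI scores are collected throughout. The recording rule in 6.1 is a minimum, and its parenthesis could be read as delaying the reduced regime until all MTD-relevant collection is over.

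Most of this stands. A reader might infer that late bladder events will go unseen, or that the table estimates real losses; the documents support neither. What remains is the record. None of these provisions changes the recording timeframe, which 8.2 assigns to 6.1, and the 90-day sentence in 6.1 goes against the lenient reading of the parenthesis. Questionnaire scores carry no CTCAE grade or attribution.

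**Arm 1 shows that the system works.** Both level 2 events (transient Grade 3 haematuria and Grade 3 incontinence) were identified and acted on. A reader might infer that the Arm 1 MTD is compromised; it is not. Section 1.2.5 does not say whether those events were serious, so their capture does not show that 6.1 required it.

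**Escalation is over.** This is true, and it removes the first consequence of the rule. The second, setting the MTD one level lower, is not withdrawn anywhere. That it still applies to Arm 2 is a reading of 3.1.1, since 1.2.5 expands level 2 without naming it the MTD.

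**Two MTD definitions?** Sections 3.1.2 and 10.1 mention only the 3-week assessment, so a reader might infer a competing MTD. That goes too far: 3.1.1 is an express exception, 10.4.4 refers back to it, 10.4.1 sets no window, and 1.2.5 discloses the basis and timing of the Arm 1 decision.

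**Conclusion.** The point holds as a conflict between two stated rules. A non-serious late Grade 3 bladder event attributable to SBRT can help determine the MTD under 3.1.1, yet 6.1 does not require it to be recorded. The required record can therefore be incomplete for an event that determines the MTD.

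The practical exposure is narrow: the Arm 2 MTD label at level 2, where two qualifying patients would move it to 40 Gy. At that level the documents report no bladder event approaching the criterion; 1.2.5 puts Arm 2 urinary toxicity at no more than Grade 2 when the expansion was decided.

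The size is unknown. The tabled losses are upper limits that rest on an assumed non-serious share, assumed or borrowed event rates, independence, and a site that records nothing beyond the minimum. Confidence is high in the textual mismatch and low in any particular effect on the reported MTD.

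**What to change.** Add one sentence to 6.1: through the 24-month follow-up, record every bladder event of Grade 3 or worse and every bowel event of Grade 4 or worse that is possibly, probably or definitely attributable to SBRT, whether or not it is serious.

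The cost is an amendment and slightly more adverse event recording at visits already scheduled. Treatment does not change.

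Optional tidying in the same amendment, not part of the error: refer to the 3.1.1 exception in 3.1.2 and 10.1, and correct the description of the bladder criterion change in 3.1.1, which should run from Grade 4 to Grade 3.
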